#### 6.8.1.2 Drugs That May Have Their Plasma Concentrations Altered by PCI-32765

In vitro studies indicated that PCI-32765 is not a substrate of P-glycoprotein (P-gp), but is a mild inhibitor (with an  $IC_{50}$  of 2.15  $\mu\text{g/mL}$ ). PCI-32765 is not expected to have systemic drug-drug interactions with P-gp substrates. However, it cannot be excluded that PCI-32765 could inhibit intestinal P-gp after a therapeutic dose. There is no clinical data available. Therefore, to avoid a

potential interaction in the GI track, narrow therapeutic range P-gp substrates such as digoxin should be taken at least 6 hours before or after PCI-32765

### **6.8.1.3 Concomitant Use of Antiplatelet Agents and Anticoagulants**

Warfarin or other vitamin K antagonists should not be administered concomitantly with PCI-32765. Supplements such as fish oil and vitamin E preparations should be avoided. Use PCI-32765 with caution in subjects requiring other anticoagulants or medications that inhibit platelet function. Subjects with congenital bleeding diathesis have not been studied. Ibrutinib should be held at least 3 to 7 days pre- and post-surgery depending upon the type of surgery and the risk of bleeding (see [Section 6.7.3](#)).

Subjects requiring the initiation of therapeutic anticoagulation therapy (eg. atrial fibrillation), consider the risk and benefit of continuing PCI-32765 treatment. If therapeutic anticoagulation is clinically indicated, treatment with ibrutinib should be held and not be restarted until the subject is clinically stable and has no signs of bleeding. Subjects should be observed closely for signs and symptoms of bleeding. No dose reduction is required when study drug is restarted.

### **6.8.2 Reproductive Toxicity**

Reproductive toxicity studies have not been conducted with PCI-32765. Therefore, women of childbearing potential, who are sexually active, must use highly effective contraception (as listed in [Section 5.2](#)) during the study and for 30 days after the last dose of study drug. Men who are sexually active, must use highly effective contraception during the study and for 90 days (3 months) after the last dose of PCI-32765. Subjects should promptly notify the investigator if they, or their partner, become pregnant during this period. If a female subject becomes pregnant during the treatment period, she must discontinue study drug immediately. Pregnancy in a female subject or a male subject's partner must be reported in the same manner as an SAE ([Section 9.3.5](#)).

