--	--

	
stomach or small bowel, or complete bowel obstruction.
 
28. History of prior malignancy, with the exception of the following:
 
 
a. Malignancy treated with curative intent and with no known active disease present for more than 3 years prior to screening and felt to be at low risk for recurrence by treating physician;
 
b. Adequately treated non-melanoma skin cancer or lentigo maligna without current evidence of disease; or
 
c. Adequately treated breast or cervical carcinoma in situ without current evidence of disease.
 
 
29. Peripheral neuropathy Grade <math>\geq 2</math> on clinical examination within 14 days prior to enrollment.
 
30. Uncontrolled diabetes mellitus.
 
31. Currently active systemic fungal, bacterial, viral, or other infection not controlled (defined as exhibiting ongoing signs/symptoms related to the infection and without improvement, despite appropriate antibiotics or other treatment).
 
32. Use of antibiotics for treatment of infection within 7 days prior to first dose of study drug.
 
33. Known history of infection with human immunodeficiency virus (HIV) or history of active infection with hepatitis C virus (HCV) or hepatitis B virus (HBV) or any uncontrolled active systemic infection.
 
34. History of stroke or intracranial hemorrhage within 6 months prior to the first dose of study drug.
 
39. Requires anticoagulation with warfarin or equivalent vitamin K antagonists (eg, phenprocoumon).
 
40. Requires treatment with strong CYP3A4/5 inhibitors (see Appendix 2)
 
Ethical/Other:
 
35. Subject is pregnant or breastfeeding.
 
36. Will not agree to use highly effective contraception (eg, condoms, implants, injectables, combined oral contraceptives, some intrauterine devices [IUDs], sexual abstinence, or sterilized partner) during the study and for 30 days after the last dose of study drug. (Note: applies to women of child-bearing potential or men with female partners of child-bearing potential only.)
 
37. Any other life-threatening illness, medical condition, or organ system dysfunction that, in the investigator’s opinion, could compromise the subject’s safety, or put the study outcomes at undue risk.
 
38. Any medical or psychiatric condition that, in opinion of investigator, could interfere with the subject’s ability to give informed consent, compliance, or treatment.

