39. Requires anticoagulation with warfarin or a vitamin K antagonist (eg, phenprocoumon).
40. Requires treatment with strong CYP3A4/5 inhibitors (see [Appendix 2](#)).

*Ethical/Other*

35. Subject is pregnant or breastfeeding.
36. Will not agree to use highly effective contraception (eg, condoms, implants, injectables, combined oral contraceptives, some intrauterine devices [IUDs], sexual abstinence, or sterilized partner) during the study and for 30 days after the last dose of study drug. (Note: applies to women of childbearing potential or men with female partners of childbearing potential only.)
37. Any other life-threatening illness, medical condition or organ system dysfunction that, in the investigator's opinion, could compromise the subject's safety, or put the study outcomes at undue risk.
38. Any medical or psychiatric condition that, in opinion of investigator, could interfere with the subject's ability to give informed consent, compliance, or treatment.

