### 9.3.5 Pregnancy

Before study enrollment, subjects must agree to take appropriate measures to avoid pregnancy. However, should a pregnancy occur (including female partners of male subjects), consent to provide follow-up information regarding the outcome of the pregnancy and the health of the infant until 30 days old will be requested.

A female subject must immediately inform the investigator if the subject becomes pregnant from the time of consent to 30 days after the last dose of study drug or a male subject must immediately inform the investigator if the subject's partner becomes pregnant from the time of consent to 3 months after the last dose of study drug. Any female subjects receiving PCI-32765 capsules who become pregnant must immediately discontinue the use of study drug. The investigator should counsel the subject, discussing any risks of continuing the pregnancy and any possible effects on the fetus.

Although pregnancy itself is not regarded as an AE, the outcome will need to be documented. Report any pregnancy that occurs in a subject or subject's partner from the time of consent to 30 days after the last dose of study drug. Record any occurrence of pregnancy on the Pregnancy Report Form Part I and email or fax to Pharmacyclics Drug Safety, or designee, within 24 hours of learning of the event. The pregnant female will be followed for outcome, which is defined as elective termination of the pregnancy, miscarriage, or delivery of the fetus. For pregnancies with an outcome of live birth, the newborn infant will be followed until 30 days old by completing the Pregnancy Report Form Part II. Any congenital anomaly/birth defect noted in the infant must be reported as a SAE.

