Serum Free Light Chain (Freelite ® )	X	X					Repeat every cycle if M protein initially or becomes not measurable by protein electrophoresis														X	X	
M-Protein (SPEP or UPEP) f	X	X					X	X	X	X	X	X	X	X	X	X	X	X	X				
Cytokines/Chemokines g		X	X	X	X		X	X	X		X					X				X			
Peripheral Blood Cellular Immunophenotyping h		X	X	X	X		X	X	X		X					X				X			
Bone Turnover Tests (serum CTX and urine NTX)		X			X		X	X	X		X		X			X				X			
Confirmation of Response u							X	X	X	X	X	X	X	X	X	X				X			
Plasmacytoma Evaluations	X	As clinically indicated v																					
Long-term Follow-up Status																					X		

Abbreviations: aPTT = activated partial thromboplastin time; CR = complete response; CT = computed tomography, CTX = C-terminal cross-linking protein of type-1 collagen; ECG = electrocardiogram; FLC = free light chain; IFE = immunofixation; Ig = immunoglobulin; INR = international normalized ratio; ECOG = Eastern Cooperative Oncology Group; LTFU = long-term follow-up; MM = multiple myeloma; MR = minimal response; NTX = N-terminal cross-linking protein of type-1 collagen; PD = progressive disease; PE = physical examination; PEP = protein electrophoresis; PR = partial response; PT = prothrombin time; RFU = response follow-up; sCR = stringent complete response; SFU = safety follow-up; SPEP = serum protein electrophoresis; UPEP = urine protein electrophoresis; VGPR = very good partial response.

- a. Study visits will occur every other cycle beginning Cycle 12 (ie Cycle 12, 14, 16, etc).
- b. The Safety Follow-up visit will occur 30 days (±7 days) from the last dose of study drug or prior to the start of a new anticancer therapy. If subject withdraws consent to treatment, subject may still participate in safety follow-up.
- c. Subjects who permanently discontinue from the study for reasons other than PD will be followed every 2 months until PD or use of alternative antineoplastic therapy. During this period, myeloma assessment will be done per investigator discretion as referenced in [Section 7.1.4](#).

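### Men agree at entry to 30 days of contraception after the last dose but must use it for 90, and the partner-pregnancy reporting window has the same 60-day shortfall

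*Protocol*

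**What the plan says.** Four places in the protocol set a period after the last dose that applies to men.

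- **Section 5.2, exclusion criterion 36.** A subject is excluded if he or she will not agree to highly effective contraception "during the study and for 30 days after the last dose of study drug. (Note: applies to women of childbearing potential or men" whose partners could become pregnant. Men are therefore inside the 30-day wording.
- **Synopsis, exclusion criterion 36.** The same period is given, and the note again "applies to women of child-bearing potential or men with female partners of child-bearing potential only".
- **Section 6.8.2.** Women have 30 days. Sexually active men must continue "for 90 days (3 months) after the last dose of PCI-32765". The section says that a partner's pregnancy is to be reported in the way an SAE is, and points to Section 9.3.5.
- **Section 9.3.5.** A male subject must inform the investigator at once if his "partner becomes pregnant from the time of consent to 3 months after the last dose of study drug". The next paragraph tells the site to report a pregnancy in a subject or subject's "partner from the time of consent to 30 days after the last dose of study drug". The report form, the 24-hour deadline and the follow-up of outcome and newborn are set out after that sentence.

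**The concern.** The protocol gives two different answers to each of two safety questions: how long a man must use contraception, and how long a partner's pregnancy stays reportable. The women's period is 30 days throughout, so only men and their partners are affected.

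Criterion 36 is what the site checks with the subject at entry. It is also the only place that lists acceptable contraceptive methods, and Section 6.8.2 sends the reader there for them. A man counselled from that text could reasonably understand that 30 days is enough.

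On reporting, an investigator told on day 60 of a new partner pregnancy was owed that notification, but the reporting sentence does not cover the event. Its outcome and the newborn's follow-up could then be missed. The protocol states that reproductive toxicity studies have not been done and bases the contraception rule on that. Without such data, pregnancies that do occur need to be captured.

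**Working it through.** The check is a comparison of texts; the only arithmetic is the difference between periods. Section 6.8.2 itself equates 3 months with 90 days.

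| Question | Shorter period | Longer period | Difference |
|---|---|---|---|
| Contraception, men | 30 days (criterion 36, Section 5.2 and synopsis) | 90 days (Section 6.8.2) | 90 − 30 = 60 days |
| Partner pregnancy | Site reports to 30 days (Section 9.3.5) | Subject notifies to 3 months (Section 9.3.5) | 90 − 30 = 60 days |
| Contraception, women | 30 days (criterion 36) | 30 days (Section 6.8.2) | 0 |
| Pregnancy in a female subject | Site reports to 30 days (Section 9.3.5) | Subject notifies to 30 days (Section 9.3.5) | 0 |

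The next question is whether any other provision closes days 31 to 90.

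1. **Section 6.8.2, reporting duty.** It states no 30-day limit of its own, but it sends the reader to Section 9.3.5, where the limit is 30 days.
2. **Section 9.3.1, AE and SAE reporting.** The period ends 30 days after the last dose. Later SAEs are reported only if considered related, and Section 9.3.5 says that pregnancy itself is not an AE.
3. **Safety Follow-up visit (Section 7.1.3; Appendix 4, footnote b).** "The Safety Follow-up visit will occur 30 days" from the last dose, with a margin of 7 days either way.
   - Earliest within the window: 30 − 7 = day 23, which is 90 − 23 = 67 days before day 90.
   - Latest within the window: 30 + 7 = day 37, which is 90 − 37 = 53 days before day 90.
   - The visit may also be brought forward before a new therapy. It can then fall before day 23, which lengthens the interval.
4. **Later contacts (Section 7.1.4; Appendix 4, footnotes c and d).** Response follow-up, about every 2 months, is for disease assessment. Long-term follow-up records survival and later therapy, and only one such visit is required. Neither lists pregnancy.
5. **Study completion (Section 7.3).** The study can close when the last active subject completes the Safety Follow-up visit. For a man in that position, closure can come before his 90 days end.

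None of these aligns the two contraception periods or brings partner pregnancies on days 31 to 90 within the reporting sentence.

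**The case against.** The best defence is that criterion 36 is only an entry test, while Section 6.8.2 is the conduct rule and is explicit. A man who follows 90 days satisfies both, and agreeing to 30 days at entry breaches nothing. That is correct, and Section 6.8.2 does bind men whatever they agreed at entry. What remains is that the commitment obtained at entry covers only 30 of the 90 days required after the last dose.

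On reporting, there is text that favours capture:

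- Section 6.8.2 requires partner pregnancies to be reported like an SAE.
- Section 9.3.5 opens by saying that consent to follow-up will be requested for any pregnancy, including one in a partner, and gives no time limit.
- A congenital anomaly in the infant must be reported as an SAE.

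This shows what was intended, and a careful investigator might well report. But the only sentence that sets a reporting window says 30 days, and nothing says which text prevails.

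It is also fair to say that the Safety Follow-up visit is not necessarily the last contact, that the consent form may already state 90 days, and that the matter leaves the endpoint, sample size and error rates untouched. These points limit the consequence. They do not remove the conflict, and a correct consent form would not repair the reporting sentence.

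**Conclusion.** The concern holds. For men, the entry criterion is 60 days shorter than the conduct rule. For partner pregnancies, the reporting window is about 60 days shorter than the notification window in the same section. Following the reporting sentence as written would leave partner pregnancies on days 31 to 90 unreported.

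The conclusion rests on current protocol text and on treating 3 months as 90 days, as Section 6.8.2 does. Three limits apply: the number of men affected is not given, the periods are precautionary and no particular hazard on days 31 to 90 is asserted, and the consent form was not available. The point should be fixed as a matter of subject safety and pregnancy capture. It has no bearing on the analysis of the clinical benefit response rate.

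**What to change.** Adopt 90 days for men, since Section 6.8.2 and the notification rule in Section 9.3.5 both point to it.

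- **Criterion 36, Section 5.2 and synopsis:** state 30 days after the last dose for women of childbearing potential, and 90 days for men with female partners of childbearing potential.
- **Section 9.3.5, reporting sentence:** keep 30 days for pregnancy in a female subject, and extend reporting of a partner's pregnancy to 3 months after the last dose.
- **Consent form:** confirm that it gives the same periods, and correct it if it does not.
- **Subjects:** inform men who are on treatment or within 90 days of their last dose.

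The cost is wording in three places, a consent form check and a note to sites. Nothing in the statistical analysis changes.

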### **6.8.3 Overdose Instructions**

Any dose of study drug administered in excess of that specified in this protocol is considered to be an overdose. Signs and symptoms of an overdose that meet any SAE criterion must be reported as an SAE in the appropriate time frame and documented as clinical sequelae to an overdose ([Section 9.3.3](#)).

There is no specific experience in the management of ibrutinib overdose in patients. No MTD was reached in the Phase 1 study in which subjects received up to 12.5 mg/kg/day (1400 mg/day). Healthy subjects were exposed up to single dose of 1680 mg. One healthy subject experienced reversible Grade 4 hepatic enzyme increases (AST and ALT) after a dose of 1680 mg. Subjects who ingested more than the recommended dosage should be closely monitored and given appropriate supportive treatment.

Refer to [Section 9.3](#) for further information regarding AE reporting.

## 7.0 STUDY PROCEDURES

The Schedule of Assessments is provided in [Appendix 4](#).

Descriptions of the scheduled evaluations are outlined below and complete information on study drug and dosing is provided in [Section 6.0](#).

Before study entry, throughout the study, and at the follow-up evaluation, various clinical and diagnostic laboratory evaluations are outlined. The purpose of obtaining these detailed measurements is to ensure adequate safety and tolerability assessments. Clinical evaluations and laboratory studies may be repeated more frequently if clinically indicated.

### 7.1 Description of Procedures

#### 7.1.1 Screening Assessments

All routine laboratory and clinical screening assessments must be performed within 21 days before the first administration of study drug, unless otherwise indicated (longer windows allowed for baseline radiologic studies). All study-specific assessments that are not part of standard-of-care must be done after subjects sign the ICF.

The following are required:

**Confirmation of Eligibility:** Perform all necessary procedures and evaluations to document that the subject meets each eligibility criterion ([Section 5.0](#)). De-identified copies of measurable disease as documented by SPEP, serum FLC and UPEP is required prior to enrollment.

Multiple myeloma diagnosis will be confirmed as well as the stage at original diagnosis and current disease status (relapsed or relapsed and refractory) will be documented if all requisite clinical results are available. Please refer to the study manual for a more detailed description of the enrollment procedures.

**Medical History:** Collect and record the subject's complete medical history through review of medical records and by interview. Concurrent medical signs and symptoms must be documented to establish baseline severities. A disease history, including the date of initial diagnosis and list of all prior anticancer treatments, and responses and duration of response to these treatments, also will be recorded.

**Concomitant Medications and Therapy:** All concomitant medications and procedures will be collected within 14 days prior to the start of study drug. Prior use of denosumab and bisphosphates should also be recorded.

**Physical Examination, Vital Signs, Height, and Weight:** The screening physical examination (PE) will include, at a minimum, the general appearance of the subject, height (screening only)

and weight, and examination of the skin, eyes, ears, nose, throat, lungs, heart, abdomen, extremities, musculoskeletal system, nervous system, and lymphatic system.

Vital signs (blood pressure, heart rate, respiratory rate, and body temperature) will be assessed after the subject has been resting in the sitting position for at least 3 minutes.

**ECOG Performance Status:** The ECOG index is provided in [Appendix 1](#).

**Electrocardiogram:** Subjects should be in the supine position for at least 10 minutes prior to the Screening ECG; 12-lead ECGs should be done in triplicate ( $\geq 1$  minute apart). The calculated QTc average of the 3 ECGs must be  $< 470$  msec for eligibility.

**Neuropathy and Bone Pain Assessments:** Subjects will complete questionnaires for neuropathy and bone pain at screening.

**Bone Marrow Aspirate and Biopsy:** A unilateral bone marrow aspirate and biopsy documenting percent marrow involvement will be done at screening. Bone marrow aspiration and biopsy are to be evaluated for morphology locally. Samples will be sent to a central laboratory for further evaluation. Refer to [Section 4.3](#) for a list of correlative assessments to be performed.

Testing will be performed at the study center's local laboratory or other clinical laboratory listed on the investigator's Form FDA 1572. De-identified copies of all bone marrow aspirate/biopsy results must be provided to the Sponsor.

**Other Laboratory Tests:** Hematology and serum chemistry are part of the screening procedures to ensure eligibility. For a description of these tests, refer to [Section 7.1.2](#).

**Urinalysis:** Screening urinalysis includes pH, ketones, specific gravity, bilirubin, protein, blood, and glucose. Testing will be performed at the study center's local laboratory or other clinical laboratory listed on the investigator's Form FDA 1572.

**Urine Pregnancy Test:** Pregnancy tests are required only for women of childbearing potential. If positive, pregnancy must be ruled out by ultrasound to be eligible for participation in the study.

**Coagulation Studies:** Measurement of PT, INR, and aPTT are part of the screening procedures. Testing will be performed at the study center's local laboratory or other clinical laboratory listed on the investigator's Form FDA 1572.

**Bone Radiological Assessment:** A radiologic skeletal survey for evaluation of bone lesions is required. Magnetic resonance imaging (MRI) and computed tomography scans are to be performed as clinically indicated, ie, for subjects with known plasmacytoma. Bone radiological assessment includes a lateral radiograph of the skull, antero-posterior and lateral views of the

spine, and antero-posterior views of the pelvis, ribs, femora, and humeri. Bone radiological assessments are to be done within 30 days prior to the first dose of study drug.

**Myeloma Specific Tests:** Myeloma-specific tests will be performed on or within 14 days prior to Cycle 1 Day 1. Serum and urine protein electrophoresis are part of the screening procedures to ensure eligibility, and quantitative immunoglobulins. Serum Free Light Chain (Freelite®), immunofixation (IFE), and  $\beta$ 2-microglobulin are required as baseline tests. For a description of these tests, refer to Section 7.1.2. Testing will be performed at the study center's local laboratory or other clinical laboratory listed on the investigator's Form FDA 1572.

**Plasmacytoma Evaluation:** Presence of plasmacytomas using standard techniques should be evaluated at screening.

